8.1.7 Drugs interactions

Not known; are being presently investigated.

8.2 CYT107 Presentation and Packaging

CYT107 is supplied as a sterile colorless liquid in 2 cc glass vials that are packed individually in cardboard box. Labels are stuck on vial and box.

The labeling is following local and GMP rules. The detailed description of labeling is provided in the Pharmacy Manual.

8.3 CYT107 Storage Accountability and Return of Unused Product

Study product will be stored frozen at -20°C until used.

The investigator, his/her designee, or hospital pharmacist must maintain complete records of all study products received, stored and subsequently dispensed.

Study product is Revimmune property; at the conclusion of the study, all unused study drug must be returned to Revimmune or designee. All unused product should be kept in suitable storage conditions until shipped. Unused product should not be used on non-study patients.

The detailed procedures to be followed by Clinic and Pharmacy are provided in the Pharmacy Manual.

8.4 Study Drug Administration

Each dose of CYT107 or Placebo will be administered in the hospital by a trained research nurse or PI. CYT107 or Placebo will be administered by intramuscular route at the dose of 10 µg/kg based on the patient's ideal body weight unless the patient meets criteria for subcutaneous injection (see Sect 4.2 Study Treatment).

The volume to be administered will be identical in all groups: 0.005mL/kg: ex: 0.375mL for patients of 75kg. The control group will receive the same volume of saline, dosing to IBW.

The detailed procedures to be followed by Pharmacy and hospital are provided in the Pharmacy Manual including a table of volumes to be administered per patient total body weight.

8.5 Duration of treatment

- Patient randomized in the “CYT107 High Frequency Arm” will receive CYT107 treatment at 10µg/kg at days 1, 4, 8, 11, 15, 18, 22, 25
- Patient randomized in the “CYT107 Low Frequency Arm” will receive CYT107 treatment at 10µg/kg at days 1, 4, 8, 15, 22 and placebo (NS: NaCl 0.9%) at days 11, 18 and 25.
- Patient randomized in the “CONTROL Arm” will receive Placebo (NS: NaCl 0.9%) at days 1, 4, 8, 11, 15, 19, 22 and 25.

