Study Treatment	
Each dose of CYT107 will be administered in the ICU or hospital setting. If the patients are discharged from the hospital at which treatment was begun, they will not receive additional treatment with CYT107.
 
CYT107 will be administered by the intramuscular route at the dose of 10µg/kg based on the patient's ideal body weight, twice a week for the first week, followed by:
 
 • Once a week for the low frequency regimen • Twice a week for the high frequency regimen • *Control is a placebo (denoted by "P") and is the saline diluent. To maintain blinding, all 3 combinations, i.e., low and high frequency CYT107 and placebo are administered at the same frequency. 
  
 	Week 1	Week 2	Week 3	Week 4	
 
 days	1	4	8	11	15	18	22	25	
   
 CYT107 - High	X	X	X	X	X	X	X	X	
 
 CYT107 - Low	X	X	X	P	X	P	X	P	
 
 Placebo	P	P	P	P	P	P	P	P	
  
		Week 1		Week 2		Week 3		Week 4		days	1	4	8	11	15	18	22	25	CYT107 - High	X	X	X	X	X	X	X	X	CYT107 - Low	X	X	X	P	X	P	X	P	Placebo	P	P	P	P	P	P	P	P
	Week 1		Week 2		Week 3		Week 4																																							
days	1	4	8	11	15	18	22	25																																						
CYT107 - High	X	X	X	X	X	X	X	X																																						
CYT107 - Low	X	X	X	P	X	P	X	P																																						
Placebo	P	P	P	P	P	P	P	P																																						

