A staggered approach to CYT107 treatment will be used in which treatment will not be initiated in a newly enrolled patient until 24 hours after the previously enrolled patient has received the second dose of CYT107 without evidence of serious adverse event (SAE) occurrence. In cases of a suspected adverse event, a scheduled dose will be postponed by 3 days to allow the adverse event to resolve. For any severe or serious adverse event during the treatment period (as judged by the Investigator), dosing will be suspended and the DSMB will be consulted for case review and advice as to termination of treatment.

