schematic "preliminary study" design																																																		
	Week 1							Week 2							Week 3							Week 4					Week 5				Week 6																			
days	1	2	3	4	5	6	7	8	9	10	11	12	13	14	15	16	17	18	19	20	21	22	23	24	25	...	28	29	...	35	36	...	42																	
IL-7	X			X				X			X				X			X				X			X																									
	X			X				X			P				X			P				X			P																									
PBO	P			P				P			P				P			P				P			P																									
ALC	X			X				X			X				X			X				X			X			X					X												X					
	TREATMENT																												FOLLOW UP																					
	IL-7 admin in 10 patients "high frequency dosing"																																																	
	IL-7 admin in 10 patients "low frequency dosing"																																																	
	10 Placebo Controls																					determination of ALC recovery and IL-7 clinical tolerance																												
	Absolute Lympho Counts																																																	

Dosing regimen for CYT107 in septic patients showed administration details of the “high frequency dosing” – (shown in red color) or the low frequency dosing (shown in blue color). The ALC is quantitated weekly throughout 6 weeks duration. Given that CYT107 will boost host immunity, we predict that patients treated with CYT107 will have decreased incidence of new secondary infection, decreased hospital readmissions (which generally are due to new secondary infections), and improved 60 day, 90 day, 180 days and one year mortality. Thus, these parameters will be recorded in all patients. The 60 day, 90 day, and one year data will be obtained by telephone interview, physician records, or by interrogating appropriate databases and newspaper obituary records. The patients will not have to be seen in clinic.

Additional experimental details:

- Patients with severe sepsis and organ failure who are admitted to the ICU are candidates. Septic patients who are not being treated in the ICU are not candidates for study enrollment.
- Septic patients will continue to receive the CYT107 to complete the full dose schedule even if their sepsis has resolved if they remain in the acute care hospital setting. Patients will not receive additional doses of CYT107 if they are discharged from the hospital.

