8.7 BLINDING

8.7.1 Organization of Blinding

The study will be performed in a double-blind manner. The patient, the investigator and study center staff will be blinded to study drug allocation. The pharmacist will be unblinded to study drug and will prepare study treatment or placebo for a patient as specified by the randomization scheme.

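### Section 8.5 puts the control arm's sixth placebo injection on day 19; every other schedule shown in the protocol has day 18

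*Protocol*

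**What the plan says.** Protocol section 8.5 lists the injection days arm by arm:

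- High frequency: CYT107 "at days 1, 4, 8, 11, 15, 18, 22, 25".
- Low frequency: CYT107 on days 1, 4, 8, 15 and 22, with "placebo (NS: NaCl 0.9%) at days 11, 18 and 25".
- Control: placebo "at days 1, 4, 8, 11, 15, 19, 22 and 25".

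The dosing calendar also appears in the synopsis (Study Treatment table) and in Figure 8 of section 4.2. The synopsis explains that, for blinding, "low and high frequency CYT107 and placebo are administered at the same frequency". On who knows the allocation, section 8.7.1 states: "The pharmacist will be unblinded to study drug and will prepare study treatment or placebo". The patient, the investigator and the centre staff are blinded.

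**The concern.** Two of the three arms in section 8.5 share one calendar and the third differs by one digit. No text gives a reason for a different control day, and the design uses placebo injections so that the arms look alike.

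Blinded staff cannot schedule by arm, so the discrepancy can do harm only through the pharmacist, who prepares syringes by randomised arm. If the pharmacist worked from section 8.5 as printed, the sixth syringe would arrive on day 18 for both CYT107 arms and on day 19 for control. A nurse or investigator who noticed the pattern could then infer control assignment for patients still in hospital and on study drug.

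There is a smaller compliance point. Section 9.2.1.1 treats noncompliance with study treatment as a major deviation, and section 9.2.1.2 restricts the per-protocol set to patients treated consistently with the protocol. With two printed days for the same injection, a control patient dosed on either one departs from part of the protocol. No window for dosing days appears in the text available, although the Appendix 2 flow chart, which is not shown, may give one.

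**Working it through.** This is a comparison of calendars; no power or error-rate calculation is involved. The inputs are the three bullets of section 8.5, the synopsis dosing table, and Figure 8 with each mark read against its day header.

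**Day of the sixth injection**

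| Source | High frequency | Low frequency | Control |
|---|---|---|---|
| Synopsis table | 18 | 18 | 18 |
| Figure 8 | 18 | 18 | 18 |
| Section 8.5 | 18 | 18 | **19** |

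The placebo row of Figure 8 has a mark under day 18 and nothing under day 19. Of the nine arm-by-source entries, eight give day 18 and one gives day 19. The synopsis table and Figure 8 each use a single day header for all arms. Counted as distinct statements of the day, there are two headers plus three lists, and four of the five give day 18.

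**Spacing between injections**

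- Days 1, 4, 8, 11, 15, 18, 22, 25: gaps of 3, 4, 3, 4, 3, 4, 3.
- Days 1, 4, 8, 11, 15, 19, 22, 25 (control in section 8.5): gaps of 3, 4, 3, 4, 4, 3, 3.

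A regular twice-weekly calendar, with injections on the first and fourth day of each of four weeks, gives 1, 4, 8, 11, 15, 18, 22, 25. That is every list except the control list in section 8.5.

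**What is unchanged.** The control list still has eight injections. Days 15 and 19 both fall in week 3 (days 15 to 21), so there are still two per week. The conflict is therefore with the listed days and not with the synopsis sentence on equal frequency. Only the sixth entry differs, by 19 − 18 = 1 day.

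**The case against.** The strongest reply is that this is a self-correcting misprint with no demonstrated consequence. The two bullets directly above it and two schedule displays make the intended day plain.

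The route to harm is also narrow. Section 8.1.6 allows thawed product to be kept for no more than 12 hours, so syringes are prepared close to use. A pharmacist holding to day 19 would probably have to decline a day 18 request from staff working to the common calendar, and the mismatch would surface. The documents do not, however, say how doses are requested. On what governs dispensing, section 8.4 says "The detailed procedures to be followed by Pharmacy and hospital are provided in the Pharmacy Manual", and that manual may already give day 18.

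Even if day 19 were followed, the signal would be imperfect. For a suspected adverse event in any arm, section 2.4.3.3 provides that "a scheduled dose will be postponed by 3 days to allow the adverse event to resolve", a larger shift than the one day at issue. The primary outcome is a laboratory lymphocyte count, secondary infections are judged by a separately blinded panel (section 10.3), patients discharged earlier receive no further doses, and assessments before day 18 are untouched.

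All of this stands and limits the weight of the point. It does not remove the error: nothing in the documents corrects section 8.5, which is the arm-specific dosing schedule in the drug section and not background text. The Appendix 2 flow chart may also carry dosing days, so the tally covers only the schedules that can be seen.

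**Conclusion.** The inconsistency is real and the text is wrong as written, with high confidence. Its size is one injection of eight, in one arm of three, displaced by one day. It has no bearing on sample size, power, the number of doses or the day 42 endpoint.

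Severity is minor. Any effect on blinding assumes that dispensing follows section 8.5 literally, that patients are still in hospital and on study drug at days 18 to 19, and that blinded staff notice the timing. The number of such patients cannot be derived from the documents, so none is given, and nothing here suggests that unblinding occurred. That day 18 is the intended day is an inference, but the other lists and the regular spacing leave no plausible alternative.

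**What to change.** In section 8.5, change 19 to 18 for the control arm, so that all three arms share days 1, 4, 8, 11, 15, 18, 22 and 25. Confirm that the Pharmacy Manual and the dosing worksheets use day 18 for every arm, and check the Appendix 2 flow chart if it lists dosing days. If dosing has already taken place, look through the dispensing records for control doses on day 19.

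The cost is one digit in the protocol and a short document check.

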8.5.1 Dose Adjustment According to Patient’s Weight

8.5.1.1 Obese Persons

For a patient with a Body Mass Index (BMI) over 30, a corrected weight will be used to calculate the final dose the patient will receive.

The corrected weight will be calculated as follows:

Corrected weight (kg) = $30 \times \text{height}^2$ (in m)

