
Secondary Biological Activity Study Endpoints
	
1) To determine pharmacokinetics (PK) including Cmax, area under the curve,(AUC) and T^{1/2} life of CYT107 in patients with severe sepsis and multiple organ failure who are treated with 10 µgs/kg ideal body weight using 2 different dosing regimens
 
2) Assessment of CYT107 immunogenicity by detection and quantification of binding antibodies and detection of neutralizing antibodies in positive samples
 
3) To determine pharmacodynamics (PD) including effects of CYT107 therapy to:
 
 i) improve absolute numbers and function of immune effector cells ii) changes in the absolute numbers of CD4+ and CD8+ T cells over the study period, standardized on the duration in the study. iii) Changes in the expression of the CYT107 receptor (CD127) on the surface of CD4+ and CD8+ T cells. iv) Effects of CYT107 on circulating monocyte HLA-DR expression v) Effects of CYT107 on whole blood LPS-stimulated TNF-α vi) Effects of CYT107 on anti-CD3/anti-CD28 stimulated peripheral blood mononuclear cells to produce IFN-γ. 
4) To determine effect of CYT107 to decrease the incidence of secondary infections. CYT107 has been highly effective in clinically relevant bacterial and fungal animal models of sepsis.(16)(18) We will compare the effect of CYT107 to reduce hospital-acquired secondary infections in CYT107 treated septic patients versus a control group of septic patients who receive placebo. The rate of hospital-acquired secondary infections at 42 days is roughly 35-40%.(20) We speculate that CYT107 will reduce the rate of secondary infections from 35-40% % to 25%.

---	--

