2.4.3.2 Dose

To date, CYT107 has not been tested in patients with sepsis. Septic patients frequently have decreased kidney and liver function, changes in circulating blood volume, and loss of vascular integrity with leakage of proteins into the interstitial space.(2) These alterations might impact the pharmacokinetics and pharmacodynamics of CYT107. Thus, we will administer CYT107 using a protocol that is highly similar to a previously protocol that was effective in improving the ALC in patients with cancer, HIV and HCV infections and was well tolerated with a low incidence of serious adverse effects. (12-14)

The dose of 10 μ g/kg, ideal body weight, administered either once or twice a week, will be evaluated in this study. CYT107 at a dose of 10 and 20 μ g/kg once a week has shown an excellent safety profile and biological activity in previous studies in HIV and oncology patients. (12-14, 32)

2.4.3.3 Dosing frequency:

Specificities of CYT107/CYT107R α pathway regulation and data gathered now in humans favor injections once a week and short therapeutic cycles. According to monkey and human data, a three to seven day interval between each injection of CYT107 should lead to full

recovery of CYT107R α expression (CD127) at the surface of T cells which responded to a previous dose of CYT107. Furthermore, a sustained response of T cells to CYT107 should be fully restored, as measured one week later by Ki-67 expression. A weekly interval was successfully tested in the HIV and post HSCT studies aimed at inducing an immune reconstitution- Short cycles, limited to 4 weeks, should avoid inducing exhaustion of T cells responsiveness to high doses of CYT107, which could occur despite the recovery of CD127 expression.

In the specific case of sepsis, there is a real urgency to allow the patients recovering an adequate number of T lymphocytes. Accordingly we will use a twice a week regimen for the very first week of treatment in both groups. Although the recovery of the CYT107 receptor at day 4 is not 100%, it is sufficient to re-stimulate the pool of T cells available for expansion. In the low frequency group we will use this twice a week regimen for the first week only, while it will be used for the full 4 weeks cycle in the high frequency group.

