4.2 Study Treatment

Up to thirty patients may be enrolled at 4 sites in the US, i.e., Vanderbilt, Ohio State, University of Florida, and Washington University School of Medicine, however, it is anticipated that the initial enrollment of 30 subjects will occur at Vanderbilt, Washington University and Limoges in France. (Note: the French sites may also enroll up to 30 patients such that a total of 30 evaluable patients will be available from the two countries). In the event that patient accrual is delayed in one country, all patients will be recruited from either the US or France alone. A computerized protocol will implement permuted block randomization in blocks of size three. This scheme ensures balance across the treatment groups for every third randomization. A maximum of 20 septic patients will be treated with CYT107 at a dose of 10µg/kg. There will be two dosing regimens as illustrated in Figure 8 (below). CYT107 will be administered intramuscularly at the dose of 10µg/kg (IBW), once or twice a week for a four week cycle. Ten septic patients will have CYT107 administered twice a week for 4 weeks. Ten septic patients will have two doses of CYT107 administered during the first week followed by one dose of CYT107 in conjunction with 1 dose of placebo for 3 additional weeks. Ten septic patients will receive placebo twice a week for four weeks along with routine standard of care per the clinical providers.

At approx. 48-120 hrs **after admission** for sepsis, those septic patients who meet the Inclusion/Exclusion criteria (see previous section) and provided written informed consent, will be entered into the study. The first dose of CYT107 (as indicated below) is at approx. 48-120 hrs after sepsis onset. The initial dose of study drug will be administered only in the ICU by the PI or research nurse. If patients have an INR greater than 2.5 or a platelet count less than 35,000, CYT107 will be administered by the subcutaneous route rather than by intra-muscular injection.

A staggered approach to CYT107 treatment will be used in which treatment will not be initiated in a newly enrolled patient until 24 hours after the previously enrolled patient has received the second dose of CYT107 without evidence of serious adverse event (SAE) occurrence.

In patients with coagulopathy (INR greater than 2.5 or a platelet count less than 35,000), CYT107 will be administrated subcutaneously.

Figure 8 Schematic study design of CYT107 Protocol

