8.1.6 CYT107 Preparation

Syringes containing the CYT107 dose (placebo dose same volume of NaCl 0.9%) will be prepared by the hospital pharmacy and delivered to the clinic in a blinded fashion. The product

should be defrosted at least 1 hour before administration. Defrosted product (and possibly put in syringe) should be kept refrigerated at +4°C/+8°C until use and for no more than 12 hours.

CYT107 ampoule will only be used if the solution is clear (following visual inspection), the vial is undamaged and the use by (expiration) date (if marked on the vial) has not been passed.

Based on patient's ideal body weight on day of study entry, the appropriate number of vials of CYT107 drug product will be prepared and administered. CYT107 will be kept refrigerated until time of immediate administration to the patient. To minimize the chance for contamination, sterile or septic technique should be carefully observed during CYT107 solution preparation (filling of the syringe) and administration.

A vial is restricted for use by a single patient. Take no more than 0.5 mL into the syringe. The dose to be injected will be divided as necessary into multiple intramuscular injections so that each injection will not exceed 0.5 ml in volume. (Dosing guidelines for ideal body weight make the requirement for multiple injections highly unlikely).

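### The protocol doses on ideal body weight, but its obesity rule (8.5.1.1) switches to the weight at BMI 30, which raises the dose instead of limiting it

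*Protocol*

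**What the plan says.** Ideal body weight is the stated basis almost everywhere the dose appears.

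- Synopsis, Study Treatment: 10 µg/kg on "ideal body weight, twice a week for the first week, followed by" the two regimens. The synopsis PK endpoint uses the same basis.
- Section 2.4.3.2: 10 µg/kg "ideal body weight, administered either once or twice a week, will be evaluated in this study".
- Section 4.2: 10 µg/kg, marked as IBW.
- Section 8.1.6: vials are prepared from "ideal body weight on day of study entry".
- Section 8.4: the same basis for active drug, and for placebo "The control group will receive the same volume of saline, dosing to IBW".

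Two passages depart from this.

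- Section 8.5.1.1: for BMI over 30, "a corrected weight will be used to calculate the final dose the patient will receive". The formula is 30 × height² (height in metres).
- Section 8.4 also says that the Pharmacy Manual holds "a table of volumes to be administered per patient total body weight".

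No section defines ideal body weight or says which rule prevails.

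**The concern.** For a patient with BMI over 30, the ideal-weight rule and 8.5.1.1 give different doses. The natural way to reconcile them is to let the specific rule override the general one: ideal weight up to BMI 30, corrected weight above it. Each patient then has a single dose once a formula for ideal weight is fixed, but the correction runs backwards. Two patients of equal height, one just below and one just above BMI 30, have the same ideal weight, yet the second receives a step increase. A weight of 30 × height² works as a cap only when the starting point is actual weight.

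Two things are at stake, both in patients with BMI over 30.

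- **Exposure.** They would receive more drug per kg of ideal weight than the protocol states. Section 2.4.3.2 says that CYT107 has not been tested in sepsis and that its PK and PD may be altered there.
- **PK.** Section 4.3.2 lists clearance, which is calculated from dose, and 3.2.1 intends the PK results to guide dosing in a larger trial. With about ten patients per arm, an unintended dose step in a few of them can blur the exposure data.

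**Working it through.** **Inputs from the protocol**

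- Dose 10 µg/kg (8.4)
- Concentration 2 mg/mL (8.1.3)
- At most 0.5 mL per injection (8.1.6)
- Corrected weight 30 × height² above BMI 30 (8.5.1.1)
- Eight doses (high frequency) or five doses (low frequency) of CYT107 (8.5)

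**Assumption.** Ideal weight is B × height² with B between 20 and 25. The documents give no formula.

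**The plan's own figure.** Volume per kg = 10 µg ÷ 2,000 µg/mL = 0.005 mL. For 75 kg this is 0.375 mL. Both match 8.4.

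**Ratio of doses.** (30 × height²) ÷ (B × height²) = 30/B, so height cancels.

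| Ideal weight at BMI | Ratio | Increase |
|---|---|---|
| 20 | 1.50 | 50% |
| 22 | 1.36 | 36% |
| 24 | 1.25 | 25% |
| 25 | 1.20 | 20% |

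The direction holds for any ideal weight set below BMI 30. Only the size depends on B.

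**Example at 1.75 m (height² = 3.0625)**

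| | 8.5.1.1 | Ideal, BMI 20 | Ideal, BMI 25 |
|---|---|---|---|
| Dosing weight (kg) | 91.9 | 61.3 | 76.6 |
| One dose (µg) | 919 | 613 | 766 |
| Eight doses (µg) | 7,350 | 4,900 | 6,125 |
| Five doses (µg) | 4,594 | 3,063 | 3,828 |

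The step on crossing BMI 30 is 919 − 766 = 153 µg to 919 − 613 = 306 µg per dose.

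**Weekly dose, twice-weekly arm.** 2 × 10 × 1.2 = 24 to 2 × 10 × 1.5 = 30 µg per kg of ideal weight, in place of 20. Section 2.3.1.3 reports 20 µg/kg/week as having the most favourable balance of efficacy and safety in HIV patients, and 30 µg/kg/week as the highest weekly dose tested there. It does not state the weight basis.

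**Clearance.** Apparent clearance is dose ÷ AUC. If the nominal ideal-weight dose is used when 1.2 to 1.5 times that amount was given, the result is 1/1.2 = 0.83 to 1/1.5 = 0.67 of the true value, an understatement of 17% to 33%.

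**A check that does not use the 20% to 50% range.** The 0.5 mL limit holds 1 mg, which is the dose for 100 kg. Under 8.5.1.1 that weight is reached at √(100/30) = 1.83 m, so every obese patient taller than this needs a second vial and a second injection. With ideal weight at BMI 25 it is reached only at √(100/25) = 2.00 m. Section 8.1.6 expects multiple injections to be very rare under ideal-weight dosing, which fits the second threshold better than the first.

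**If the total-weight table were used for dosing.** At actual BMI 35 the ratio to ideal weight is 35/25 = 1.40 to 35/20 = 1.75. The excess is larger and grows with BMI.

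**The case against.** The strongest reply is that the sponsor meant actual weight capped at BMI 30. The heading of 8.5.1 speaks of adjustment to the patient's weight, the Pharmacy Manual table is described as being by total body weight, and the worked example in 8.4 names 75 kg without calling it ideal. On that reading nothing jumps at BMI 30, and obese patients receive less per actual kg: 10 × 30/35 = 8.6 µg at BMI 35 and 10 × 30/40 = 7.5 µg at BMI 40. This is a plausible account of where the formula came from. But no dosing section states actual weight, and 8.4 contradicts it for the placebo volume. If it is the intent, the ideal-weight wording is the error and must go.

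Other points carry weight.

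- The Pharmacy Manual is not available here and may define ideal weight or state precedence. That would not remove the conflict in the protocol. The table reference in 8.4 is itself a loose cross-reference, not a dosing rule.
- The clearance error arises only if the nominal dose is analysed. Nothing says it would be, and the dispensing records required by 8.3 should allow the amount given to be recovered. Clearance appears in 4.3.2 but not in the PK lists of the synopsis, 3.2.1 or 7.2.
- No safety harm is shown. Even at BMI 20, the 30 µg per kg of ideal weight per week does not exceed the highest weekly dose tested in HIV, and the single dose of 15 µg/kg is half the 30 µg/kg maximum tolerated single dose reported in 2.3.1.3.
- Volume and rule are the same in all arms, so randomisation, blinding and the primary lymphocyte comparison are not biased by this.

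**Conclusion.** The concern holds. The protocol contains two dosing rules that conflict for patients with BMI over 30. Applied as written, the obesity rule increases their dose relative to the stated 10 µg/kg of ideal weight. The direction is certain for any ideal weight below BMI 30. The size, 20% to 50% per dose, rests on taking ideal weight as BMI 20 to 25. The clearance error of 17% to 33% is conditional on using the nominal dose. The documents do not give the share of patients with BMI over 30, so the number affected among the 20 patients planned for CYT107 in 4.2 is unknown. This should be fixed: it changes the dose that some patients receive in a first use in sepsis, although it does not threaten the comparison between arms.

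**What to change.** Choose one weight basis and use it throughout.

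1. Preferred: keep ideal body weight, state its formula in 8.4, and delete 8.5.1.1.
2. If the sponsor intends actual weight capped at BMI 30: replace the ideal-weight wording in the synopsis, 2.4.3.2, 4.2, 8.1.6 and 8.4, and keep 8.5.1.1 as the cap.
3. In either case, change the reference to total body weight in 8.4, and the Pharmacy Manual table itself, to the chosen basis.
4. Record the dosing weight and the µg given at each dose in the CRF, and report PK per dose actually given.

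The cost is wording changes in the protocol and Pharmacy Manual plus two CRF fields. Body weight is already collected at examination (7.1), and dispensing records are already required (8.3).
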